## **11. MEASUREMENT OF EFFECT**

Tumor response will be assessed by MRI (or CT, if MRI contraindicated) every 8 weeks (+/- 1 week) for patients treated on this study using iRANO criteria as outlined below. Clinicians may repeat response assessment more frequently as clinically indicated.

Local radiologic assessment of tumor measurements will be used during the study for clinical management and investigator-assessed disease progression. Cases of suspected radiologic disease progression will be confirmed by an MRI (or CT, as applicable) performed approximately 12 weeks after the initial radiological assessment of progression.

### **11.1 Antitumor Effect – Definitions**

- 11.1.1 Evaluable for toxicity.** All participants who receive at least one dose of study treatment will be evaluable for toxicity from the time of their first treatment.
- 11.1.2 Evaluable for objective response.** Only those participants who have measurable disease present at baseline (obtained within 14 days of cycle 1, day 1) scan and have received at least one dose of therapy will be considered evaluable for response. These participants will have their response classified according to the definitions stated below. (Note: Participants who exhibit objective disease progression or die prior to the end of cycle 1 will also be considered evaluable.)
- 11.1.3 Measurable disease.** Bi-dimensionally, contrast-enhancing, measurable lesions with clearly defined margins by CT or MRI scan, with a minimal diameter of 1 cm, and visible on 2 axial slices which are at least 5 mm apart with 0 mm skip. Measurement of tumor around a cyst or surgical cavity, if necessary, requires a minimum thickness of 3 mm. If there are too many measurable lesions to measure at each evaluation, the investigator must choose the largest two to be followed before a participant is entered on study. The remaining lesions will be considered non-measurable for the purpose of objective response determination. Unless progression is observed, objective response can only be determined when all measurable and non-measurable lesions are assessed.
- 11.1.4 Non-measurable evaluable disease.** Unidimensionally measurable lesions, masses with margins not clearly defined, lesions with maximal diameter < 1cm.

CONFIDENTIAL

This document is confidential. Do not disclose or use except as authorized.

## 11.2 Efficacy Assessments (Response/Progression Categories)

The primary efficacy measure of the study is progression-free survival at 6 months (PFS-6). PFS-6 is defined as the proportion of participants in the analysis population who remain progression-free for at least six months following initiation of study therapy. OS will be followed continuously while subjects are on study drug and every 3 months via in-person or phone contact during the survival follow-up phase of the study (see Section 5.2).

Investigator-assessed tumor response will be based upon iRANO criteria. Tumor assessments will be performed at baseline and then every 8 weeks (+/- 1 week) thereafter. Radiologic response will be assessed by comparing the pretreatment baseline and on-treatment MRI scans. Radiologic progression will be determined by using the smallest tumor measurement at either the pretreatment baseline or after initiation of study medication. Table 11.2-1 describes the radiologic and clinical criteria that will be used for determining tumor response.

Table 11.2-1 iRANO Criteria for Response Assessment Incorporating MRI and Clinical Factors	
Response	Criteria
Complete Response	
Requires all of the following:
 
 
• Complete disappearance of all enhancing measurable and non-measurable disease sustained for at least 4 weeks;
 
• No new lesions;
 
• Stable or improved non-enhancing (T2/FLAIR) lesions;
 
• Patients must be off corticosteroids (or on physiologic replacement doses only);
 
• And stable or improved clinically.
 
 
Note: Patients with non-measurable disease only cannot have a complete response; the best response possible is stable disease.

Partial Response	
Requires all of the following:
 
 
• <math>\geq 50\%</math> decrease compared with baseline in the sum of products of perpendicular diameters of all measurable enhancing lesions sustained for at least 4 weeks;
 
• No progression of non-measurable disease;
 
• No new lesions;
 
• Stable or improved non-enhancing (T2/FLAIR) lesions on same or lower dose of corticosteroids compared with baseline scan;
 
• The corticosteroid dose at the time of the scan evaluation should be no greater than the dose at time of baseline scan;
 
• And stable or improved clinically.
 
 
Note: Patients with non-measurable disease only cannot have a partial response; the best response possible is stable disease.

CONFIDENTIAL

This document is confidential. Do not disclose or use except as authorized.

Response	Criteria
Stable Disease	
Requires all of the following:
 
 
• Does not qualify for complete response, partial response, or progression;
 
• Stable non-enhancing (T2/FLAIR) lesions on same or lower dose of corticosteroids compared with baseline scan.
 
 
In the event that the corticosteroid dose was increased for new symptoms and signs without confirmation of disease progression on neuroimaging, and subsequent follow-up imaging shows that this increase in corticosteroids was required because of disease progression, the last scan considered to show stable disease will be the scan obtained when the corticosteroid dose was equivalent to the baseline dose.

Progressive Disease	
Defined by any of the following:
 
 
• <math>\geq 25\%</math> increase in sum of the products of perpendicular diameters of enhancing lesions compared with the smallest tumor measurement obtained either at baseline (if no decrease) or best response, on stable or increasing doses of corticosteroids*;
 
• Significant increase in T2/FLAIR non-enhancing lesions on stable or increasing doses of corticosteroids compared with baseline scan or best response after initiation of therapy* not cause by co-morbid events (eg, radiation therapy, demyelination, ischemic injury, infection, seizures, postoperative changes, or other treatment effects);
 
• Any new lesion;
 
• Clear clinical deterioration not attributable to other causes apart from the tumor (eg, seizures, medication adverse effects, complications of therapy, cerebrovascular events, infection, and so on) or changes in corticosteroid dose; failure to return for evaluation as a result of death or deteriorating condition;
 
• Or clear progression of non-measurable disease.
 
 
Confirmation of radiographic progression should be performed on follow-up imaging for participants who are not developing significant neurologic decline felt to be attributable to underlying tumor growth as detailed in Section 11.4.

\* Stable doses of corticosteroids include subjects not on corticosteroids

Abbreviations: MRI, magnetic resonance imaging; FLAIR, fluid-attenuated inversion recovery

For purposes of this study, the minimum time from baseline for determination of SD will be 4 weeks.

CONFIDENTIAL

This document is confidential. Do not disclose or use except as authorized.

The iRANO Response Criteria to be used in this study are summarized in Table 11.2-2.

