### **6.3 Criteria to Resume Treatment**

Criteria to resume study treatment with study medication previously meeting dose delay criteria:

Participants may resume treatment with study drug(s) when the drug-related AE(s) resolve to Grade  $\leq 1$  or baseline value, with the following exceptions:

- Participants may resume treatment in the presence of Grade 2 fatigue
- Participants who have not experienced a Grade 3 drug-related skin AE may resume treatment in the presence of Grade 2 skin toxicity
- Participants with baseline Grade 1 AST/ALT or total bilirubin who require dose delays for reasons other than a 2-grade shift in AST/ALT or total bilirubin may resume treatment in the presence of Grade 2 AST/ALT OR total bilirubin
- Participants with combined Grade 2 AST/ALT AND total bilirubin values meeting discontinuation parameters (Section 6.4) should have treatment permanently discontinued
- Drug-related pulmonary toxicity, diarrhea, or colitis, must have resolved to baseline before treatment is resumed
  - Participants with persistent Grade 1 pneumonitis after completion of a steroid taper over at least 1 month may be eligible for retreatment after prospective discussion with and approval from the study's Overall PI, [name], or selected designee.
- Drug-related endocrinopathies adequately controlled with only physiologic hormone replacement may resume treatment

If the criteria to resume treatment are met, the participant should restart treatment at the next scheduled time point per protocol. However, if the treatment is delayed past the next scheduled timepoint per protocol, the next scheduled timepoint will be delayed until dosing resumes.

CONFIDENTIAL

This document is confidential. Do not disclose or use except as authorized.

If treatment with study medication is delayed  $> 6$  weeks, the participant must be permanently discontinued from study therapy, except as specified in Section 6.4.

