  - Grade 4 drug-related endocrinopathy adverse events, such as adrenal insufficiency, ACTH deficiency, hyper- or hypothyroidism, or glucose intolerance, which resolve or are adequately controlled with physiologic hormone replacement (corticosteroids, thyroid hormones) or glucose-controlling agents, respectively, may not require discontinuation after prospective discussion with and approval from the study's Overall PI, [name] or designee.
- Any dosing interruption lasting  $> 6$  weeks from the last dose with the following exceptions:
  - Dosing interruptions to allow for prolonged steroid tapers to manage drug-related adverse events are allowed. Prior to re-initiating treatment in a participant with a dosing

CONFIDENTIAL

This document is confidential. Do not disclose or use except as authorized.

interruption lasting > 6 weeks, the study's Overall PI, [name] or designee must be consulted and approve of the plan. Tumor assessments should continue as per protocol even if dosing is interrupted.

- If Treating Investigator wants to hold drug for > 6 weeks for non-drug-related reasons, the study's Overall PI, [name] or designee must provide approval prior to re-initiating treatment. Tumor assessments should continue as per protocol even if dosing is interrupted.
- Any adverse event, laboratory abnormality, or intercurrent illness that, in the judgment of the Investigator, presents a substantial clinical risk to the subject with continued nivolumab or ipilimumab dosing.

For Cohort 2 – Patients who experience AEs while receiving nivolumab plus ipilimumab combination therapy that meet criteria for discontinuation of nivolumab/ipilimumab combination therapy may resume study therapy with nivolumab monotherapy once they fully recover as long as they are benefiting from study therapy and it is felt to be medically appropriate by the treating physician. However, if a patient experiences a clinically significant recurrence in any of the aforementioned toxicities, nivolumab monotherapy will be permanently discontinued.

Study treatment must be discontinued upon confirmed radiologic progression or clinical progression (whichever comes first) as described in Section 11.2.

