**Table 11.2-2 Summary of the RANO Response Criteria**

	CR	PR	SD	PD#
T1-Gd +	None	≥50% decrease	<50% decrease- <25% increase	≥25% increase*
T2/FLAIR	Stable or decrease	Stable or decrease	NA	NA
New Lesion	None	None	None	Present*
Corticosteroids	None	Stable or decrease	Stable or decrease	Stable or increasing
Clinical Status	Stable or increase	Stable or increase	Stable or increase	Decrease*
Requirement for Response	All	All	All	Any*

CR=complete response; PR=partial response; SD=stable disease; PD=progressive disease;  
NA= not applicable

#: Progression occurs when any of the criteria with \* is present

Increase in corticosteroids alone will not be taken into account in determining progression in the absence of persistent clinical deterioration

Of note, patients who require increased corticosteroids within two weeks of MRI assessment (relative to the dose taken at the time of the prior assessment) cannot be classified as CR, PR or SD and should be classified as non-evaluable at that time point. Conversely, patients who decrease corticosteroids within two weeks of MRI assessment (relative to the dose taken at the time of the prior assessment) cannot be classified as PD and should be classified as non-evaluable.

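### Tables 11.2-1 and 11.2-2: new or increased physiologic corticosteroid replacement blocks a partial response but not a complete one, and the two tables disagree on complete response (minor; secondary ORR only)

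*Combined protocol and SAP*

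**What the plan says.** Protocol Section 11.2 sets the response categories in Table 11.2-1 and summarises them in Table 11.2-2. The corticosteroid conditions are:

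- **CR, Table 11.2-1:** "Patients must be off corticosteroids (or on physiologic replacement doses only").
- **PR, Table 11.2-1:** "The corticosteroid dose at the time of the scan evaluation should be no greater than the dose at time of baseline scan". All listed PR conditions must be met.
- **SD, Table 11.2-1:** "Stable non-enhancing (T2/FLAIR) lesions on same or lower dose of corticosteroids compared with baseline scan".
- **Table 11.2-2:** the corticosteroid row gives none for CR, and stable or decreasing for PR and SD. No column mentions physiologic replacement.
- **Note under Table 11.2-2:** "patients who require increased corticosteroids within two weeks of MRI assessment (relative to the dose taken at the time of the prior assessment") cannot be rated CR, PR or SD at that scan and are non-evaluable there. The same section says that a steroid increase alone is not progression.

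Section 11.5 requires a PR to be seen at consecutive assessments at least 4 weeks apart. It scores as SD anyone without CR, PR or confirmed progression. Section 14.1.2.2 defines ORR as confirmed CR or PR over response-evaluable subjects.

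On treatment, Section 6.3 states: "Drug-related endocrinopathies adequately controlled with only physiologic hormone replacement may resume treatment". Section 6.4 has a similar allowance, subject to approval, for Grade 4 endocrine events "which resolve or are adequately controlled with physiologic hormone replacement (corticosteroids, thyroid hormones").

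**The concern.** A limit on corticosteroids in response criteria keeps steroid treatment of edema from passing as tumor response. Physiologic replacement is a different use, and the CR row already treats it so. The PR and SD rows do not carry that exception.

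The situation is foreseeable. Section 7.1.1 lists adrenal insufficiency and hypopituitarism for both drugs, and Section 2.2.4 says that adverse events are more frequent and more severe with the combination. Patients on replacement may stay on study drug and therefore stay under response assessment.

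At stake is the secondary endpoint ORR. Responders would be lost in one direction only. Response is assessed by investigators in an open-label trial. Without a written rule, one investigator may apply the text and another may disregard replacement doses after seeing the scan.

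**Working it through.** The plan states no ORR target, no endocrinopathy rate and no replacement rate, so there is no figure to reproduce. The check is a reading of the criteria, followed by an illustrative range.

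**Step 1. The same steroid history under each row.** Take a patient off corticosteroids at the baseline scan who starts lasting physiologic corticosteroid before any PR is confirmed.

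| Finding at a later scan | Table 11.2-1 | Table 11.2-2 |
|---|---|---|
| Complete disappearance | CR permitted | CR not permitted |
| At least 50% shrinkage | PR not permitted (dose above baseline) | PR not permitted (dose not stable or lower) |
| Neither response nor progression | SD not permitted | SD not permitted |

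The first row shows the conflict between the tables. The second row shows the asymmetry: a smaller tumor effect fails on a steroid condition that the larger effect passes.

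**Step 2. What happens to the lost PR.** Without CR, PR or confirmed progression, the Section 11.5 fallback gives SD. A patient who later progresses is SD if an SD scan was recorded before replacement began. In neither case is the patient in the ORR numerator, and the patient stays in the denominator. The bias can only be downward. Scheduled scans are 8 weeks apart, so replacement that starts between a first PR scan and the confirming scan also voids that PR.

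**Step 3. Who is not affected.**

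- Patients whose baseline dose was equal or higher. Section 3.2.5.2 allows some systemic corticosteroid and physiologic replacement at entry.
- Patients replaced with thyroid hormone only, which is not a corticosteroid.
- Patients whose PR was confirmed before replacement started.
- Patients with complete disappearance, under Table 11.2-1.

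The two-week note compares with the prior assessment, so a stable replacement dose does not trigger it at later scans.

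**Step 4. Other endpoints.** A steroid increase alone is not progression, so PFS-6 has no route to a material change. Duration of response (Section 14.1.6.1) runs from response to progression or death, and starting replacement is neither. Losing a responder changes who is included, but nothing in the documents shows in which direction.

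**Step 5. Illustrative size.** Let p be the true PR rate and f the share of PRs that fail only because physiologic corticosteroid is new or raised before confirmation. Both are assumptions. Take n = 25, the planned cohort size in Section 14.1.4, with all patients response-evaluable.

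- Expected PRs lost = 25 × p × f
- ORR loss = p × f
- Chance of losing at least one = 1 − (1 − p × f)^25

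| p | f | PRs lost | True PR rate → rate as scored | Loss (points) | Chance of at least one lost |
|---|---|---|---|---|---|
| 5% | 2% | 0.025 | 5% → 4.9% | 0.1 | 2.5% |
| 10% | 10% | 0.25 | 10% → 9% | 1 | 22.2% |
| 20% | 10% | 0.5 | 20% → 18% | 2 | 39.7% |
| 30% | 20% | 1.5 | 30% → 24% | 6 | 78.7% |

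One lost PR among 25 evaluable patients is 1/25 = 4 points of observed ORR, and more if fewer patients have measurable disease at baseline.

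**The case against.** The strongest reply is that a loss needs several things together: a partial rather than complete response, replacement by corticosteroid, a dose above baseline, and a start before confirmation. ORR is secondary and descriptive. The decision rules in Sections 14.1.4 and 14.1.5.1 use progression-free status only. Section 5.9.4 already allows steroid use to be analyzed against outcomes. All of this stands and sets the severity at minor.

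The reply also notes that some Cohort 1 outcomes were known when Cohort 2 was added (Section 2.4), so relaxing PR now would be a data-aware change that favors a higher ORR. That stands too, and the fix allows for it. The tables are presented as iRANO/RANO criteria, and whether the asymmetry departs from the source cannot be judged from these documents. The internal conflict on CR does not depend on the source.

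Three stronger readings are tempting, and the documents do not support them:

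- **That a patient on hormone replacement can never be rated PR.** The limit is relative to the baseline dose, and Step 3 lists the exceptions.
- **That 1 to 5 of 25 responses would be lost.** An assumed 5-20% of patients needing replacement gives 1.25 to 5 patients exposed to the rule, not lost responders.
- **That Cohort 1 ORR could fall from 1/25 to 0/25.** Section 2.4 reports one near complete response by personal communication. It gives no ORR denominator, and nothing says that this patient received replacement.

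**Conclusion.** The defect is real but narrow. The criteria misclassify a foreseeable case, at least 50% shrinkage with physiologic corticosteroid new or raised relative to baseline before PR is confirmed, and the two tables contradict each other on CR. The effect on ORR is downward. Its size cannot be known from the documents. Under the assumed ranges above it is 0.025 to 1.5 PRs per cohort, or 0.1 to 6 points. Best response of SD is largely protected by the Section 11.5 fallback, PFS-6 is not materially affected, and no direction of bias in duration of response is shown. Severity: minor, secondary endpoint only.

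**What to change.** 1. In the PR and SD rows of Table 11.2-1, state that physiologic replacement doses do not count toward the corticosteroid dose compared with baseline.
2. In the note under Table 11.2-2, state that starting or adjusting physiologic replacement is not a corticosteroid increase.
3. Reconcile the CR cell of Table 11.2-2 with the CR row of Table 11.2-1.
4. Apply the change prospectively, and report ORR for each cohort under both the current and the revised wording as a sensitivity analysis.

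The cost is a short amendment and one extra ORR summary. No new data are needed: Section 5.9.4 and footnote p of the study calendars already collect corticosteroid name, dose, dates and reason for use.

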**Table 11.2-2 Summary of the RANO Response Criteria**

	CR	PR	SD	PD#
T1-Gd +	None	≥50% decrease	<50% decrease- <25% increase	≥25% increase*
T2/FLAIR	Stable or decrease	Stable or decrease	NA	NA
New Lesion	None	None	None	Present*
Corticosteroids	None	Stable or decrease	Stable or decrease	Stable or increasing
Clinical Status	Stable or increase	Stable or increase	Stable or increase	Decrease*
Requirement for Response	All	All	All	Any*

CR=complete response; PR=partial response; SD=stable disease; PD=progressive disease;  
NA= not applicable

#: Progression occurs when any of the criteria with \* is present

Increase in corticosteroids alone will not be taken into account in determining progression in the absence of persistent clinical deterioration

Of note, patients who require increased corticosteroids within two weeks of MRI assessment (relative to the dose taken at the time of the prior assessment) cannot be classified as CR, PR or SD and should be classified as non-evaluable at that time point. Conversely, patients who decrease corticosteroids within two weeks of MRI assessment (relative to the dose taken at the time of the prior assessment) cannot be classified as PD and should be classified as non-evaluable.

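### The steroid-decrease note under Table 11.2-2 bars PD even for a new lesion, contradicting Table 11.2-1, and the plan does not say how a non-evaluable scan counts in PFS-6

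*Combined protocol and SAP*

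**What the plan says.** Table 11.2-1 (Section 11.2) gives five routes to PD, any one of which is enough. Two carry a steroid condition: enhancing growth of at least 25% and a significant T2/FLAIR increase count only "on stable or increasing doses of corticosteroids". Clinical deterioration counts unless something else explains it, and a changed steroid dose is one of the listed explanations. The other two routes have no steroid condition: "Any new lesion" and "Or clear progression of non-measurable disease".

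Table 11.2-2 summarises the criteria and makes any single starred entry sufficient for PD. The new-lesion entry is starred; the corticosteroid row is not.

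The note below that table has a clause for patients whose steroid dose fell within two weeks of the MRI, which continues: "relative to the dose taken at the time of the prior assessment) cannot be classified as PD and should be classified as non-evaluable". It sets no minimum decrease and lists no exempt criterion. A mirror clause makes a scan non-evaluable for response or stable disease after an increase.

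Section 14.1.2.2 dates PFS at the first documented progression. For patients with only non-measurable baseline disease, it counts new lesions as progression without mentioning steroids. Section 14.1.2.1 defines PFS-6 as a proportion of the analysis population, and Section 14.2 assigns efficacy to all treated participants. None of these sections gives a rule for a non-evaluable scan, and Section 14 states that there will be no separate SAP.

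**The concern.** The same scan can be read two ways. An investigator following Table 11.2-1 calls a new lesion PD; one following the note calls the scan non-evaluable. The endpoint is investigator-assessed in an open-label study, so nothing downstream settles the difference.

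The trigger is foreseeable. Section 3.2.5.2 admits patients on up to 4 mg/day of dexamethasone, Section 5.9.4 permits systemic steroids for treatment-related events and for sequelae of meningioma treatment, and Section 6.4 says: "Dosing interruptions to allow for prolonged steroid tapers to manage drug-related adverse events are allowed".

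At stake is the primary decision. Each cohort is judged alone against a historical rate, so no concurrent control absorbs a scoring error, and the final rule in Section 14.1.4 can turn on one patient.

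**Working it through.** **1. The texts side by side.** Take a patient whose dose fell within two weeks of the MRI, relative to the prior assessment.

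| Finding on the scan or at the visit | Table 11.2-1 | Note |
|---|---|---|
| Enhancing growth of 25% or more | PD condition not met | Non-evaluable |
| T2/FLAIR increase | PD condition not met | Non-evaluable |
| New lesion | PD | Non-evaluable |
| Progression of non-measurable disease | PD | Non-evaluable |
| Clinical deterioration | PD unless explained, e.g. by the steroid change | Non-evaluable |

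The clear conflict is in rows three and four. In the first two rows both texts withhold PD.

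**2. Timing.** Scans fall every 8 weeks ± 1 week, and six months is about 26 weeks.
- Week-24 scan: weeks 23 to 25, before the mark. Next scheduled scan: weeks 31 to 33, after it. If week 24 is non-evaluable and PD is first documented at week 32, the progression date falls after six months.
- Week-8 or week-16 scan non-evaluable, PD documented by week 24: the date is before six months and the patient is a failure.

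Section 11.4 back-dates confirmed progression to when it was first determined, and Section 5.6 to when the criteria were first met. A scan barred from PD by the note does neither on the note's own terms.

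**3. The plan's figures.** Section 14.1.4 gives n = 25, success at 10 or more, null 0.26, alternative 0.51.
- P(X ≥ 10 | 25, 0.26) = 0.0893, matching the stated 0.089.
- P(X ≥ 10 | 25, 0.51) = 0.904, matching the stated 90%.
- Interim, P(X ≤ 2 | 10): 0.496 and 0.048, matching 0.5 and 0.048.
- With the interim stop enforced: alpha 0.082, power 0.880.

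**4. If masked progressors count as successes.** The documents give no rate, so these are assumptions.
- One certain false success: P(X ≥ 9 | 24, 0.26) = 0.147. Two: P(X ≥ 8 | 23, 0.26) = 0.230.
- A fraction m of all true progressors by six months is masked, so the observed null rate is 0.26 + 0.74m:

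| m | Observed null rate | Single-stage alpha | With interim stop |
|---|---|---|---|
| 0 | 0.260 | 0.089 | 0.082 |
| 2% | 0.2748 | 0.121 | 0.112 |
| 5% | 0.297 | 0.180 | 0.167 |
| 10% | 0.334 | 0.307 | 0.287 |

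Only progression first seen near week 24 matters. Assuming exponential PFS with 26% at 26 weeks, the share progressing between weeks 16 and 24 is 0.26^(16/26) − 0.26^(24/26) = 0.436 − 0.288 = 0.148, or 25 × 0.148 = 3.7 patients. The three values of m would then need 0.0148, 0.037 and 0.074 divided by 0.148, i.e. 10%, 25% and 50% of that group to be masked.

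**5. Other ways of counting a non-evaluable scan.**
- 5% or 10% of true successes counted as failures: power falls from 0.904 to 0.852 (rate 0.4845) or 0.785 (rate 0.459).
- One patient dropped, bar kept at 10: P(X ≥ 10 | 24) gives alpha 0.069 and power 0.868.

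**The case against.** The strongest reply is that the note's reach is narrow and its direction unproven. Much of that stands.

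- A reader might infer that any steroid decrease, or any scan during a taper, blocks PD. The clause needs a decrease within two weeks of the MRI, to below the dose at the prior assessment. A patient on no steroid at week 16 who starts at week 18 and is tapering at week 24 is above the prior dose and is not caught.
- A reader might infer that the plan counts non-evaluable scans as successes. No text says so. Section 14.1.5.1 speaks of evaluable patients at the interim, Section 14.2 of all treated participants, and Section 14.1.2.2 censors time-to-event PFS. Counting such a scan as success is one possible result of the gap; counting it as failure costs power instead. A bias in one direction is not established.
- Non-evaluable status attaches to one assessment. Section 11 allows earlier repeat imaging, and Section 5.6 dates pathology-confirmed progression to first suspicion. Both can recover the date, but neither is required after a steroid-related non-evaluable scan.
- Table 11.2-1 itself withholds PD for size and T2/FLAIR growth on a falling dose, so those cases are not the note's doing.
- It is tempting to quote alpha of 0.179, from P(X ≥ 9 | 25, 0.26). That supposes that one true progressor is masked in every trial. The 0.147 also supposes a certain event. Neither is an estimate.
- The tables and the note also differ on the reference dose. For partial response, Table 11.2-1 says "The corticosteroid dose at the time of the scan evaluation should be no greater than the dose at time of baseline scan", while the note looks to the prior assessment. For response and stable disease this is untidy but does not change how progression is scored.

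None of this removes the contradiction over new lesions and non-measurable disease, or supplies the missing PFS-6 rule.

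**Conclusion.** The point holds in a bounded form. The decrease clause contradicts Table 11.2-1, the starred rule in Table 11.2-2 and, for new lesions in non-measurable disease, Section 14.1.2.2. Followed as written, it can leave true progression unscored. The exposure on PFS-6 is mainly at the scan nearest six months, and it becomes a false success only if the missing rule is filled that way.

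The size is unknown. One certain false success takes single-stage alpha from 0.089 to 0.147, above the planned 0.10, but under the exponential assumption that is one of about 3.7 patients expected to progress between weeks 16 and 24 (1/3.7 = 27%). The larger values of m are hard to reach from new-lesion and non-measurable cases alone. The reason to act is that the primary endpoint has two incompatible scoring rules and no tie-breaker.

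**What to change.** Amend Sections 11.2 and 14.1.2 as follows.

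1. Limit the decrease clause to the enhancing-size and T2/FLAIR criteria. A new lesion or clear progression of non-measurable disease stays PD whatever the steroid change. Clinical deterioration keeps its existing exclusion for steroid-dose changes.
2. If a scan is non-evaluable only because of a steroid decrease and the next evaluable scan shows PD against the same reference measurement, date PD to the earlier scan. This extends the back-dating principle of Section 11.4.
3. State whether a non-evaluable six-month assessment counts in PFS-6 as success, failure or exclusion, for the interim and final rules alike, and give the resulting operating characteristics.

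Apply the rule to both cohorts. Section 2.4 already describes Cohort 1 outcomes, so report any rescoring of that cohort as a sensitivity analysis.

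The cost is a protocol amendment. No extra scan or visit is needed, and Section 5.9.4 already collects steroid doses and dates. The downside is that some progressions will be dated earlier, so PFS-6 may be slightly less favourable.
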